Patients who successfully complete the open-label run-in and continue to meet all inclusion/exclusion criteria will be randomized (1:1 ratio) on the last day of the run-in period (Day 0) to either Sequence 1 or 2. Subjects randomized to Sequence 1 will receive Treatment A (amifampridine phosphate or placebo) in Period 1 and Treatment B (the other treatment) in Period 2. Subjects randomized to Sequence 2 will receive Treatment B (amifampridine or placebo) in Period 1 and Treatment A (the other treatment) in Period 2. Study medication (amifampridine phosphate tablets or placebo tablets) for Period 1 will be dispensed on Day 0, the last day of the Run-in, by the site pharmacist, according to the randomization schedule.

The administration of blinded medication will begin only after completion of all assessments of Day 0. The Day 0 assessments are performed while taking a dose of open-label amifampridine phosphate in the clinic, 40 minutes before starting the assessments. Any supply of open-label amifampridine phosphate should be collected by the study site and stored before dispensing the Period 1 blinded medication.

The patient will receive either blinded amifampridine phosphate tablets or placebo tablets for 8 days as an outpatient, and a dose of the same medication on the day of scheduled study visit (Day 8) in the clinic, in order to facilitate efficacy assessments, under double-blind conditions. If the patient is on a BID or TID regimen during Period 1, the Day 8 assessments should occur after the same dose that corresponds to when assessments were done on Day 0. All unused medication and the container must be brought back to the study site at the end of Period 1. **The Day 8 medication is the same as double-blind medication taken for the previous Period 1 days.** Any unused portion of dispensed drug will be returned to the pharmacy before dispensing drug for the Re-Stabilization Period. A dose of medication for Day 8 must be administered by research study staff, in the clinic, in order to perform evaluations within specified time periods, as described in Section 10.3.3.

Re-stabilization Period (Days 9-21) (+1 day)

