1.3 Sample Size

The primary analysis variable is the SGI Change from Baseline (CFB). It will be analyzed using the standard analysis for a two-by-two crossover design. The sample size required to control the power depends on the ratio of the between-treatment difference and the standard deviation of the difference (that is, the effect size). Assuming an effect size of 0.5, 23 patients per sequence will ensure power of 90% for the 2-sided test at the 0.05 level.

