4.2 Analysis of Efficacy

4.2.1 Analysis of Primary Efficacy

Summary statistics for the SGI Day 0 assessment (baseline for period 1), SGI Day 8 assessment, and the corresponding change from baseline (CFB₁) will be presented by treatment and by treatment within mutation type (pre- vs. post-synaptic, see Table 2.2-1 above) as period 1. A Mann-Whitney-Wilcoxon test for equality of the CFB₁ in the two treatments in Period 1 will be presented. Summary statistics for the SGI Day 21 assessment (baseline for period 2), SGI Day 29 assessment, and the corresponding change from baseline (CFB₂) will also be presented by treatment and treatment within mutation type as period 2. Also, the change in CFB from Period 1 to Period 2 will be computed. This value estimates

$$\tau_1 - \tau_2$$

where τ_1 represents the treatment effect of the period 1 Investigational Product (IP) and τ_2 represents the treatment effect of period 2 IP. A Mann-Whitney-Wilcoxon test of the hypothesis that the above parameter is the same in both treatment sequences will be provided. Note that this is a nonparametric version of the treatment main effect in a linear model without carryover effects.

A mixed effects linear model will be fit to the data with SGI raw scores as the response. The model will include fixed effect terms for treatment, period, age group (2 to less than 6, 7 to less than 12, and 12 to less than 17 years of age, 17 years and over), mutation type and sequence*period, where sequence corresponds to the order in which the subject received treatments, and a random effect for subject. The LSMeans for the treatment groups will be calculated and provided, as will the estimated difference along with a 95% confidence interval for this difference and a formal hypothesis test that the difference in the means is 0.

Special care must be taken in crossover designs to ensure that there is not significant carryover effect; however, the pharmacological properties of amifampridine are such that

having a 12-day washout period should minimize any unequal carryover effects in the analysis.

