A mixed effects linear model will be fit to each of the MFM datasets described above with percent outcome or individual item scores (as appropriate for each dataset) as the response variable. The model will include fixed effect terms for treatment, period, age group (2 to less than 6 years, 7 to less than 12 years, 12 to less than 17 years of age, and 17 years of age and above), genetic mutation type (see Table 2.2-1), and sequence*period, where sequence corresponds to the order in which the subject received treatments, and a random effect for subject. No carryover term will be fit. In the case of the MFM percent outcome datasets for the adult only patients, the age group fixed effect term will not be included in the model. The LSMeans for the treatment groups will be calculated and provided, as will the estimated difference along with a 95% confidence interval for this difference and a formal hypothesis test that difference in the means is 0. Note that it is highly likely that some specific mutations will have insufficient subjects to fit the specified model. In that case a notation will be made in the relevant table(s) that there are not sufficient observations to fit the model.

Special care must be taken in crossover designs to ensure that there is no significant carryover effect; however, the pharmacological properties of amifampridine (an elimination half-life of 1.8-2.5 hours) are such that having a 12-day restabilization period will minimize any unequal carryover effects in the analysis.

Clinical Global Impression

CGI-S and CGI-I will be summarized by frequency tables and percentages for each sequence group and period. The values will be analyzed with a Wilcoxon rank-sum test as outlined in Putt and Chinchilli (2004). The treatment effects will be estimated using the Hodges-Lehmann estimator and a 90% asymptotic confidence interval.

Single Fiber Electromyogram

Summary statistics for mean jitter, median jitter, and percent block will be presented by treatment and visit. No formal inferential procedures will be performed for these data.

Slurp Test

Summary statistics for the time to slurp sound from the slurp test and its CFB (Day 0 for Period 1 and Day 21 for Period 2) will be presented. No formal inferential procedures will be performed for these data.

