Appendix A – Tables, Figures and Listing Specifications

Orientation

Tables and figures will be displayed in landscape.

Margins

Margins will be 1 inch on all sides. Table and listing boundaries will not extend into the margins.

Font

Courier New, 8 point.

Headers

The table number will be on the first line of the title. The title area will contain the Sponsor name, the study number, and the name of the table. The title area will contain the page number (Page x of y) on the far right, one line above the name of the table.

Footers

- The first line will be a solid line.
- Next will be any footnotes regarding information displayed in the table.
- Below these footnotes will be displayed “STATKING Clinical Services (Date)” on the far left.
- The last line will display the name of the SAS program that generated the table and (if applicable) the source data reference.

Table Disclaimer

The format of the mock tables shown in the appendix of this Statistical Analysis Plan (SAP) will be the format of the deliverable tables to the extent that Word document constructed tables can match production tables produced by SAS. This formatting includes the content and format of the header and footer areas of the tables. The Sponsor agrees to the format of the tables as shown in the appendix.

Further programming charges will be applicable for changes in the format of tables (including title statements, notes, data dependent footnotes, etc.) made after the approval of the SAP.

Missing Values

All missing values will be displayed on the output tables/listings as blanks.

Display of Study Dates

The date format to be used is yyyy-mm-dd. Missing parts of dates are not shown (i.e., for a missing day value, the value displayed is in yyyy-mm format).

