		Day 8	CFB	xxx	xxx	xxx	xxx	xxx	xxx
		Day 21 (Baseline)	RAW	xxx	xxx	xxx	xxx	xxx	xxx
		Day 29	RAW	xxx	xxx	xxx	xxx	xxx	xxx
		Day 29	CFB	xxx	xxx	xxx	xxx	xxx	xxx

^a RAW = observed data entered in the database; CFB = change from baseline = Score at time point - baseline score.
 STATKING Clinical Services (yyyy-mm-dd)
 Source Program: xxxxxxx.sas

Table format repeats for PP population.

Table 7. SGI Score Summary Mann-Whitney Main Effects Test Results
Catalyst Pharmaceuticals, Inc. - CMS-001
FAS Population (N=xxx)

Variable	Test	n	Mean Difference ^a	Test Statistic	P-Value
SGI	Period 1	xx	xxx	xxx	xxx
	Crossover	xx	xxx	xxx	xxx

^a The Period 1 mean-of-differences is the difference in mean CFB at the end of Study Period 1, corresponding to a parallel study design analysis. The Crossover mean-of-differences is the difference between the Period 1 CFB and Period 2 CFB.

STATKING Clinical Services (yyyy-mm-dd)

Source Program: xxxxxxx.sas

Table format repeats for PP population.

Page x of y

Table 9. SGI Score Mixed Model Analysis
Catalyst Pharmaceuticals, Inc. - CMS-001
FAS Population (N=xxx)

Statistic ^a	Amifampridine/ Placebo	Placebo/ Amifampridine
n	xxx	xxx
Least Squares (LS) Mean of Raw SGI Score	xxx	xxx
Between-Treatment Difference in LS Means (Amifampridine - Placebo)	xxx	
Denominator Degrees of freedom	x	
95% CI for Between-Treatment Difference in LS Means (Amifampridine - Placebo)	(xxx, xxx)	

^a Raw SGI score was modeled as the response, with fixed effects terms for treatment, period, age group, mutation type and sequence*period (i.e., carryover). Subject was treated as a random effect.

STATKING Clinical Services (yyyy-mm-dd)

Source Program: xxxxxxx.sas

Table format repeats for PP population.

Table 11. MFM-32 Score Summary Statistics by Treatment, Period and Time Point
 Catalyst Pharmaceuticals, Inc. - CMS-001
 FAS Population (N=xxx)

Treatment	Variable ^a	Period	Time Point	Data Type ^b	Std					
					Mean	Dev	n	Min	Max	Median
Amifampridine/Placebo	xxxxxxxx	1	Day 0 (Baseline)	RAW	xxx	xxx	xxx	xxx	xxx	xxx
			Day 8	RAW	xxx	xxx	xxx	xxx	xxx	xxx
				CFB	xxx	xxx	xxx	xxx	xxx	xxx
	xxxxxxxx	2	Day 21 (Baseline)	RAW	xxx	xxx	xxx	xxx	xxx	xxx
			Day 29	RAW	xxx	xxx	xxx	xxx	xxx	xxx
				CFB	xxx	xxx	xxx	xxx	xxx	xxx
Placebo/Amifampridine	xxxxxx	1	Day 0 (Baseline)	RAW	xxx	xxx	xxx	xxx	xxx	xxx
			Day 8	RAW	xxx	xxx	xxx	xxx	xxx	xxx
				CFB	xxx	xxx	xxx	xxx	xxx	xxx
	xxxxxx	2	Day 21 (Baseline)	RAW	xxx	xxx	xxx	xxx	xxx	xxx
			Day 29	RAW	xxx	xxx	xxx	xxx	xxx	xxx

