				CFB	xxx	xxx	xxx	xxx	xxx	xxx

^a This will correspond to one of the following: Dimension 1, 2, 3, the grand total, the corresponding percentages (X1, X2, X3, X), and the individual item scores.

^b RAW = observed data entered in the database; CFB = Change from baseline = Score at time point - baseline score.

STATKING Clinical Services (yyyy-mm-dd)

Source Program: xxxxxxxx.sas

Table format repeats for PP population.

Table 13. MFM-32 Score Summary Mann-Whitney Main Effects Test Results
 Catalyst Pharmaceuticals, Inc. - CMS-001
 FAS Population (N=xxx)

Scale	Test	n	Mean of Differences ^a	Test Statistic	P-Value
Total	Period 1	xx	xxx	xxx	xxx
	Crossover	xx	xxx	xxx	xxx
D-1	Period 1	xx	xxx	xxx	xxx
	Crossover	xx	xxx	xxx	xxx
D-2	Period 1	xx	xxx	xxx	xxx
	Crossover	xx	xxx	xxx	xxx
D-3	Period 1	xx	xxx	xxx	xxx
	Crossover	xx	xxx	xxx	xxx
Item xx	Period 1	xx	xxx	xxx	xxx
	Crossover	xx	xxx	xxx	xxx
Item yy	Period 1	xx	xxx	xxx	xxx
	Crossover	xx	xxx	xxx	xxx
Item zz	Period 1	xx	xxx	xxx	xxx
	Crossover	xx	xxx	xxx	xxx

^a The Period 1 mean-of-differences is the difference in mean CFB at the end of Study Period 1, corresponding to a parallel study design analysis. The Crossover mean-of-differences is the difference between the Period 1 CFB mean and Period 2 CFB mean. Individual items are sorted by the value of the test statistic associated with the crossover test.

STATKING Clinical Services (yyyy-mm-dd)

Source Program: xxxxxxx.sas

Table format repeats for PP population. Individual items will be ordered in increasing order of the p-values for the Crossover test.

Table 15. MFM-32 Score Mixed Model Analysis
 Catalyst Pharmaceuticals, Inc. - CMS-001
 FAS Population (N=xxxx)

Variable	Statistic ^a	Amifampridine/ Placebo	Placebo/ Amifampridine
Overall	n	xxx	xxx
	Least Squares (LS) Mean of Change from Baseline	xxx	xxx
	Between-Treatment Difference in LS Means (A-B)	xxx	
	Denominator degrees of freedom	x	
	95% CI for Between-Treatment Difference in LS Means (A-B)	(xxx, xxx)	
D1 Domain	n	xxx	xxx
	Least Squares (LS) Mean of Change from Baseline	xxx	xxx
	Between-Treatment Difference in LS Means (A-B)	xxx	
	Denominator degrees of freedom	x	
	95% CI for Between-Treatment Difference in LS Means (A-B)	(xxx, xxx)	
D2 Domain	n	xxx	xxx
	Least Squares (LS) Mean of Change from Baseline	xxx	xxx
	Between-Treatment Difference in LS Means (A-B)	xxx	
	Denominator degrees of freedom	x	
	95% CI for Between-Treatment Difference in LS Means (A-B)	(xxx, xxx)	
D3 Domain	n	xxx	xxx

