	95% CI for Between-Treatment Difference in LS Means (A-B)	(xxx, xxx)	

^a Raw MFM score was modeled as the response, with fixed effects terms for treatment, period, mutation type and sequence*period (i.e., carryover). Subject was treated as a random effect.
 STATKING Clinical Services (yyyy-mm-dd)
 Source Program: xxxxxxxx.sas

Table format repeats for PP population. Individual items will be ordered in increasing order of the p-values for the Crossover test.

Table 27. MFM Percent-of-Possible Score Mixed Model Analysis
 Catalyst Pharmaceuticals, Inc. - CMS-001
 FAS Population (N=xxx)

Variable	Statistic ^a	Amifampridine/ Placebo	Placebo/ Amifampridine
Overall	n	xxx	xxx
	Least Squares (LS) Mean of Change from Baseline	xxx	xxx
	Between-Treatment Difference in LS Means (A-B)	xxx	
	Denominator degrees of freedom	x	
	95% CI for Between-Treatment Difference in LS Means (A-B)	(xxxx, xxx)	
D1 Subscale	n	xxx	xxx
	Least Squares (LS) Mean of Change from Baseline	xxx	xxx
	Between-Treatment Difference in LS Means (A-B)	xxx	
	Denominator degrees of freedom	x	
	95% CI for Between-Treatment Difference in LS Means (A-B)	(xxxx, xxx)	
D2 Subscale	n	xxx	xxx
	Least Squares (LS) Mean of Change from Baseline	xxx	xxx
	Between-Treatment Difference in LS Means (A-B)	xxx	
	Denominator degrees of freedom	x	
	95% CI for Between-Treatment Difference in LS Means (A-B)	(xxxx, xxx)	
D3 Subscale	N	xxx	xxx
	Least Squares (LS) Mean of Change from Baseline	xxx	xxx
	Between-Treatment Difference in LS Means (A-B)	xxx	
	Denominator degrees of freedom	x	
	95% CI for Between-Treatment Difference in LS Means (A-B)	(xxxx, xxx)	
Item xxx	n	xxx	xxx
	Least Squares (LS) Mean of Change from Baseline	xxx	xxx
	Between-Treatment Difference in LS Means (A-B)	xxx	
	Denominator degrees of freedom	x	
	95% CI for Between-Treatment Difference in LS Means (A-B)	(xxxx, xxx)	

^a MFM score expressed as a percentage of the maximum possible was modeled as the response, with fixed effects terms for treatment, period, sequence*period (i.e., carryover) and mutation type at Baseline. Individuals measured with the MFM-20 are excluded from the analyses for items in the MFM-32 excluded from the MFM-20.

STATKING Clinical Services (yyyy-mm-dd)

Source Program: xxxxxxxx.sas

Table format repeats for PP population. Individual items will be ordered in increasing order of the p-values for the Crossover test.

Table 29. MFM Percent-of-Possible Score Mixed Model Analysis by Age Group
 Catalyst Pharmaceuticals, Inc. - CMS-001

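### The SGI and MFM mixed-model table shells print LS means by sequence instead of the treatment LS means that the SAP text promises, and the model term they carry has to change before treatment columns can be filled

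*SAP*

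**What the plan says.** For the SGI model, SAP 4.2.1 states: "The LSMeans for the treatment groups will be calculated and provided". It adds the estimated difference, a 95% confidence interval and a hypothesis test. SAP 4.2.2 makes the same promise for each MFM dataset.

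The Appendix B shells for these models are Tables 9 (SGI) and 15, 17, 23, 25, 27, 29 and 31 (MFM), each repeated for the PP population. All eight have two LS-mean columns, headed *Amifampridine/Placebo* and *Placebo/Amifampridine*. Below them is a single difference with its confidence interval. Table 9 labels it "Between-Treatment Difference in LS Means (Amifampridine - Placebo"; the seven MFM shells label it "Between-Treatment Difference in LS Means (A-B". None of the eight has a p-value row.

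On the letters A and B, Protocol 10.1 says that one sequence receives "Treatment A (amifampridine phosphate or placebo) in Period 1 and Treatment B (the other treatment) in Period 2". SAP 1.1 uses A for amifampridine and P for placebo, and has no B.

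The footnotes of Tables 23, 27, 29 and 31 describe the model "with fixed effects terms for treatment, period, sequence*period (i.e., carryover) and mutation type at Baseline" and mention no random effect. SAP 4.2.2 lists sequence*period among the fixed effects, then adds "and a random effect for subject. No carryover term will be fit". SAP Appendix A says that the format of the shells "will be the format of the deliverable tables", as far as SAS output can match them.

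**The concern.** The slash headings denote sequences. SAP 1.1 defines the two sequences this way, Tables 1 and 3 to 5 use the same labels for the randomised groups, and Table 46 heads them as treatment sequence. Where the SAP means treatment, as in Tables 41, 42, 45 and 47, it heads the columns plainly Amifampridine and Placebo.

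Built as drawn, the model-based SGI and MFM tables would show two similar means above a difference that does not follow from them. No mixed-model table would show an LS mean on amifampridine or on placebo. A programmer or reader who subtracts one column from the other gets a between-patient comparison of sequences, which carries no information on the drug. In the MFM tables the undefined letter B leaves the direction of the difference to inference.

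**Working it through.** **The plan's own figure.** SAP 1.3 says: "Assuming an effect size of 0.5, 23 patients per sequence will ensure power of 90% for the 2-sided test at the 0.05 level". Its effect size is the treatment difference divided by the SD of the difference. The normal approximation gives N = (1.960 + 1.282)² / 0.5² = 42.03, so 43 patients. With 46 patients and 44 degrees of freedom, the noncentral t gives power 0.912. The figure reproduces and is not disputed here. It concerns the within-patient treatment contrast, which the column headings do not show.

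**What each column estimates.** Let A and P be the expected scores on amifampridine and placebo, and π₁ and π₂ the period effects.

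- Sequence AP: [(A + π₁) + (P + π₂)] / 2
- Sequence PA: [(P + π₁) + (A + π₂)] / 2
- Difference: 0, whatever A − P and π₂ − π₁ are

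**Illustration.** Protocol 8.4.3 gives, for the LEMS study, an SGI of 5.9 on amifampridine and LS mean changes of −0.8 (amifampridine) and −2.6 (placebo). Using these for CMS, with 5.9 as a common starting level, is an assumption. Then A = 5.9 − 0.8 = 5.1 and P = 5.9 − 2.6 = 3.3.

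| Case | AP column | PA column | AP − PA | Amifampridine − placebo |
|---|---|---|---|---|
| Drug effect 1.8 | 4.2 | 4.2 | 0 | 1.8 |
| Drug effect 0 | 4.2 | 4.2 | 0 | 0 |
| Drug effect 4.0 | 4.2 | 4.2 | 0 | 4.0 |
| 1.8, period effect 0.5 | 4.2 | 4.2 | 0 | 1.8 |
| 1.8, sequence effect 0.4 | 4.4 | 4.0 | 0.40 | 1.8 |
| 1.8, carryover 0.5 from amifampridine | 4.45 | 4.2 | 0.25 | 1.55 |

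**Chance spread.** With an assumed between-patient SD of 1.2 and within-patient SD of 1.0, the observed column difference has SD √[2(1.2² + 1.0²/2)/n] = √(3.88/n), where n is the number per sequence. That is 0.41 at n = 23 and 0.62 at n = 10. Simulation of 20,000 trials per setting agreed, with a mean of 0.00 at drug effects of 0, 1.8 and 4.0. The printed columns will therefore differ somewhat, but not because of the drug.

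**Can relabelled columns be filled?** Take one outcome per period. There are four cells: AP period 1, AP period 2, PA period 1 and PA period 2. The sequence*period term alone has a parameter for each. The amifampridine indicator is the sum of the AP period 1 and PA period 2 indicators, so treatment adds nothing: the design has rank 4 with or without it. Age group and mutation type are constant within a patient and do not break this. The treatment LS means and their difference are then not estimable. With treatment, period and sequence instead, the difference is estimable as ½[(AP₁ − AP₂) − (PA₁ − PA₂)]. In the illustration this is ½[(5.1 − 3.3) − (3.3 − 5.1)] = 1.8.

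**Footnotes.** Those of Tables 9, 15, 17 and 25 state that subject is a random effect. Those of Tables 23, 27, 29 and 31 do not. Table 27 covers the pooled percent scores, the secondary analysis in Protocol 15.8.

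**The case against.** The strongest reply is that this is a heading slip. Section 4 of the SAP fixes the treatment contrast, its interval and its test. Table 9 prints the difference with an explicit direction, and Appendix A governs layout without saying that a shell overrides the text. The model has no sequence main effect, so sequence LS means are not its natural output, and headings carried over from other tables are a likely explanation. Moreover, the primary variable is SGI change from baseline (Protocol 15.7, SAP 1.3), whereas Table 9 models raw SGI; tests on the change scores, with p-values, are in Table 7. All of this stands, and it limits the severity. It does not remove the conflict between text and shells, which recurs in all eight tables.

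Four stronger readings are tempting, and the documents do not support them.

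- *Treatment means are missing from the whole report.* Tables 5, 11 and 19 give unadjusted means by sequence, period and day, from which each treatment can be read. Only the treatment LS means are missing.
- *The two columns always differ by zero.* Zero is an expectation without sequence or unequal carryover effects.
- *The subject effect has been dropped, at a cost in precision.* The four footnotes list fixed effects and are silent on random ones. SAP 4.2.2 requires the subject effect and the tables are titled as mixed models, so no loss of precision can be charged to the plan.
- *The sign of the MFM difference cannot be known.* SAP 4.2.2 sets the individual MFM treatment effect as amifampridine minus placebo. The direction can be inferred; the label simply fails to say it.

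**Conclusion.** The point holds as a table-specification error of moderate severity. Eight shells and their PP repeats contradict SAP 4.2.1 and 4.2.2: the LS-mean columns are by sequence, the drug effect cancels in them in expectation, and no mixed-model table shows an LS mean for either treatment. The undefined B, the missing p-value row and the four incomplete footnotes are smaller faults in the same shells.

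The equality of the columns assumes no sequence effect and no unequal carryover. The values 4.2, 5.1 and 3.3 borrow LEMS results and show the mechanism only. The non-estimability result assumes one outcome per period enters the model; on that assumption, correcting the headings alone would leave the tables unfillable.

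**What to change.** In Tables 9, 15, 17, 23, 25, 27, 29 and 31 and their PP repeats (10, 16, 18, 24, 26, 28, 30 and 32):

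1. Head the LS-mean columns Amifampridine and Placebo, with n as the number of patients contributing a score on that treatment.
2. Write every difference and its interval as Amifampridine − Placebo.
3. Add a p-value row for the test promised in SAP 4.2.1 and 4.2.2.
4. State in the footnotes of Tables 23, 27, 29 and 31 that subject is a random effect.
5. Replace sequence*period with sequence in SAP 4.2.1, SAP 4.2.2 and the footnotes. This makes the treatment LS means and their difference estimable. It also removes the clash between the footnotes, which call the term carryover, and 4.2.2, which says that no carryover term is fitted.

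The cost is an edit to two SAP sections and the shells, best made before programming and before unblinding. Nothing changes in the conduct of the trial. Appendix A notes that format changes after SAP approval carry programming charges.
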